### **9.2 Study Endpoint Definitions**

#### **9.2.1 Primary Endpoints**

##### **9.2.1.1 Composite Complete Remission (CRc) Rate**

CRc rate is defined as the proportion of patients who achieve CR or CRi according to the modified response criteria for AML (Cheson 2003) defined in Appendix E. Patients whose disease response cannot be assessed will be considered non-responders for calculating the CRc rate.

### **9.2.1.2 Overall Survival (OS)**

Overall survival (OS) is defined as the time from randomization to death due to any cause. Specifically,

$$\text{OS} = \text{Date of death} - \text{Date of randomization} + 1.$$

For a patient who is not known to have died by the end of study follow up, observation of OS is censored on the date the patient was last known to be alive (i.e., date of last contact). Patients lacking data beyond the day of randomization will have their survival time censored on the date of randomization (i.e., OS duration of 1 day).

## **9.2.2 Secondary Efficacy Endpoints**

### **9.2.2.1 MRD-negative CRc Rate**

MRD-negative CRc rate is defined as the proportion of patients who achieve both morphologic remission (CR or CRi) and MRD-negative status. Patients whose morphologic response or MRD status cannot be assessed will be considered non-responders for calculating the MRD-negative CRc rate.

### **9.2.2.2 Duration of Remission**

Duration of remission is defined as the time from the first documentation of CR or CRi to the first documentation of disease relapse or to death due to any cause, whichever comes first. Patients who have started a new antitumor therapy (excluding maintenance therapy during remission in the absence of relapse, or consolidative allogeneic or autologous stem cell transplant after study treatment) prior to documentation of disease relapse will be censored at the date of the last response assessment on or prior to start of new therapy.

Duration of remission will be calculated only for the subgroup of patients achieving a CR or CRi.

### **9.2.2.3 Event-Free Survival (EFS)**

EFS is defined as the time from randomization to the first documentation of progression, disease relapse (see [Appendix E](#)) or to death due to any cause, whichever comes first. Patients who have started an antitumor therapy (excluding maintenance therapy during remission in the absence of relapse, or consolidative allogeneic or autologous stem cell transplant after study treatment) other than the study treatment prior to documentation of progression or disease relapse will be censored at the date of the last response assessment on or prior to start of new therapy.

### **9.2.2.4 Leukemia-Free Survival (LFS)**

LFS is defined as the time from the first documentation of blast clearance (morphologic leukemia-free state [mLFS], CR or CRi) to the first documentation of disease relapse or to death due to any cause, whichever comes first (see [Appendix E](#)). Patients who have started an antitumor therapy (excluding maintenance therapy during remission in the absence of

relapse, or consolidative allogeneic or autologous stem cell transplant after study treatment) other than the study treatment prior to documentation of progression or disease relapse will be censored at the date of the last response assessment on or prior to start of new therapy.

LFS will be calculated only for the subgroup of patients achieving a CR or CRi.

#### **9.2.2.5 Time to Complete Remission**

Time to complete remission (TTCR) is defined as the time from randomization to the first documentation of CR or CRi. TTCR will be calculated only for the subgroup of patients achieving a CR or CRi.

#### **9.2.2.6 Mortality Rates**

The 30-day mortality rate is defined as the proportion of patients who die within 30 days of randomization. The 60-day mortality rate is defined as the proportion of patients who die within 60 days of randomization.

### **9.3 Statistical and Analytical Plans**

The statistical and analytical plans presented below summarize the more complete plans to be detailed in the statistical analysis plan (SAP). A change to the data analysis methods described in the protocol will require a protocol amendment only if it alters site conduct (e.g., adding baseline assessments to define a subgroup). The SAP will be finalized prior to the first interim analysis. Any changes to the methods described in the final SAP will be described and justified in the clinical study report.

#### **9.3.1 General Considerations**

##### **9.3.1.1 Randomization and Blinding**

This is a randomized study that will enroll approximately 540 patients. Patients will be randomized in a 1:1 manner to receive either vadastuximab talirine plus HMA or placebo plus HMA.

Patients will be stratified based on the following variables to ensure that patient-specific risk factors are appropriately balanced between treatment arms:

- Cytogenetic risk per revised UK MRC classification (intermediate versus adverse; see [Appendix D](#))
- ECOG performance status (0–1 versus 2)
- HMA (azacitidine versus decitabine)
- Age (<75 years versus ≥75 years)

After stratification, patients will be randomized into 1 of 2 treatment arms, for a total of approximately 270 patients per arm.

Randomization will be performed centrally using a system that will assign a unique patient randomization number. The actual treatment assignment will remain blinded. Randomization procedures are detailed in the Study Manual.

### **9.3.1.2 Adjustments for Covariates**

Stratified analyses will include adjustment for the stratification factor as recorded at randomization (described in Section 9.3.1.1). Other covariates may be considered for adjustment in exploratory analyses.

### **9.3.1.3 Handling of Dropouts and Missing Data**

Missing data will not be imputed, with the exception of AE dates while calculating duration of events and treatment-emergent status. Patients with missing values of a variable other than response endpoints (CRc rate, MRD-negative CRc rate) and time-to-event endpoints (OS, LFS, and EFS) will be excluded from the analysis of that endpoint. Patients whose disease response cannot be assessed will be scored as non-responders for calculating the CRc rate and MRD-negative CRc rate. Censoring rules will be applied to the estimation of the distribution of the time-to-event endpoints, details will be provided in the SAP.

### **9.3.1.4 Multicenter Studies**

There are multiple centers in this study, however it is not anticipated that any center will accrue enough patients to warrant an analysis by center.

### **9.3.1.5 Multiple Comparisons and Multiplicity**

To maintain strong control of the Type I error rate at 0.05, the fallback procedure proposed by Wiens will be used in the testing of the primary endpoints, with an alpha of 0.01 pre-assigned to CRc rate and an alpha of 0.04 pre-assigned to OS. (Wiens 2005). If the test for the CRc rate is statistically significant, then the alpha of 0.01 will be re-allocated to OS, and the test for OS will be performed at a 2-sided alpha of 0.05. If the test for the CRc rate is not statistically significant, then the test for OS will be performed at a 2-sided alpha of 0.04.

The parallel gatekeeping principle will be used to control the overall type I error rate of 0.05 (Dmitrienko 2011). The primary endpoints, CRc rate and OS (family 1), will be the gatekeepers for testing the secondary endpoint of MRD-negative CRc rate (family 2). If at least one of the primary endpoints is statistically significant, then a statistical test will be performed for the MRD-negative CRc rate. If both CRc rate and OS are statistically significant, then MRD-negative CRc rate will be tested at an overall alpha of 0.05. If only one of the 2 primary endpoints is statistically significant, then MRD-negative CRc rate will be tested at the corresponding alpha level of the significant primary endpoint. If the tests for both CRc rate and OS are not statistically significant, then the p-value of the test for MRD-negative CRc rate will still be calculated but will be considered descriptive.

Two formal interim analyses for OS are planned. The test significance level for OS at the interim analysis will be adjusted based on the actual number of OS events observed at each interim analysis according to the O'Brien-Fleming spending function.

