### **9.3.1.9 Timing of Analyses**

The primary analysis of CRc rate is planned when the following 2 conditions are met: 1) 6 months after 308 patients have been randomized, and 2) approximately 212 OS events have occurred. The estimated duration of the study through the primary analysis of CRc rate is approximately 2 years from randomization of the first patient based on design assumptions. Only the first 308 patients randomized will be included in the primary analysis of CRc rate. CRc rate will also be analyzed for all randomized patients at the time of the final analysis.

The estimated duration of the study through the final analysis for OS is approximately 3 years from randomization of the first patient based on design assumptions.

There are 2 planned interim analyses of OS. The first interim analysis will take place when approximately 106 OS events have occurred (~30% of the targeted number of events) and will assess the futility of vadastuximab talirine in combination with azacitidine or decitabine.

The second interim analysis for OS will occur in conjunction with the primary analysis of CRc rate. The analysis will be conducted when the following 2 conditions are met: 1) 6 months after 308 patients have been randomized, and 2) approximately 212 OS events have occurred (~60% of the targeted number of events). The interim OS results will be assessed for early stopping for efficacy.

The IDMC will provide recommendations to the sponsor's Data Review Board as to appropriate study direction at the interim analysis.

End-of-trial is defined as the point at which all patients have died or discontinued the study, or have been followed for a maximum of 3 years after the last patient enrolled, whichever comes first. An end-of-trial analysis will be performed after study closure.

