6.7 Multiple Comparison/Multiplicity

To maintain strong control of the Type I error rate at 0.05, the fallback procedure proposed by Wiens will be used in the testing of primary endpoints, with an alpha of 0.01 pre-assigned to CRc rate and an alpha of 0.04 pre-assigned to OS (Wiens 2005). If the test for the CRc rate is statistically significant, then the alpha of 0.01 will be re-allocated to OS, and the test for OS will be performed at a 2-sided alpha of 0.05. If the test for the CRc rate is not statistically significant, then the test for OS will be performed at a 2-sided alpha of 0.04.

The parallel gatekeeping principle will be used to control the overall type I error rate of 0.05 (Dmitrienko 2011). The primary endpoints, CRc rate and OS (family 1), will be the gatekeepers for testing the secondary endpoint of MRD-negative CRc rate (family 2). If at least one of the primary endpoints is statistically significant, then a statistical test will be performed for the MRD-negative CRc rate. If both CRc rate and OS are statistically significant, then MRD-negative CRc rate will be tested at an overall alpha of 0.05. If only one of the 2 primary endpoints is statistically significant, then MRD-negative CRc rate will be tested at the corresponding alpha level of the significant primary endpoint. If the tests for both CRc rate and OS are not statistically significant, then the p-value of the test for MRD-negative CRc rate will still be calculated but considered descriptive.

Two formal interim analyses for OS are planned. The test significance level for OS at the interim analysis will be adjusted based on the actual number of OS events observed at each interim analysis according to the O'Brien-Fleming spending function.

Due to safety concerns raised by the IDMC, the study was terminated early prior to the first interim analysis planned in the protocol. Final analysis will be performed based on 240 patients randomized into the study by the time enrollment was closed. All efficacy analysis will be descriptive in nature and no multiple testing procedure will be applied.

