7.5 Efficacy Analyses

All efficacy analyses will be descriptive in nature and will be presented using the ITT analysis set.

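### The gatekeeping rule does not hold the stated overall type I error of 0.05: it can reach 0.0595, because the CRc alpha of 0.01 is used for both OS and MRD-negative CRc

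*Protocol*

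**What the plan says.** Protocol 9.3.1.5 tests the two primary endpoints by a fallback procedure, "with an alpha of 0.01 pre-assigned to CRc rate and an alpha of 0.04 pre-assigned to OS". If CRc is significant, "then the alpha of 0.01 will be re-allocated to OS, and the test for OS will be performed at a 2-sided alpha of 0.05"; otherwise OS is tested at 0.04.

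MRD-negative CRc forms a second family behind the primaries, and the section states: "The parallel gatekeeping principle will be used to control the overall type I error rate of 0.05". It is tested formally if at least one primary is significant, and at 0.05 if both are. If only one is, "MRD-negative CRc rate will be tested at the corresponding alpha level of the significant primary endpoint". That means 0.01 when the one is CRc and 0.04 when it is OS.

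SAP 6.7 repeats these rules and then, because of the early termination, adds: "All efficacy analysis will be descriptive in nature and no multiple testing procedure will be applied". SAP 7.5 says the same of the efficacy analyses.

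**The concern.** Alpha released by a rejected hypothesis can be passed on once. Here all of the CRc alpha goes to OS. If OS is then not significant, none is left for MRD-negative CRc, yet the rule still tests it at 0.01. The problem is confined to this branch (CRc significant, OS not).

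The configuration that exposes it is plausible. MRD-negative CRc is "the proportion of patients who achieve both morphologic remission (CR or CRi) and MRD-negative status", so additional remissions that remain MRD-positive would raise CRc without raising MRD-negative CRc. A CRc effect without an OS effect is the situation in which having two separate primary endpoints matters. Under the procedure as designed, a formal claim on MRD-negative CRc supported only by a significant CRc would lie outside the stated 0.05.

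**Working it through.** **Inputs (Protocol 9.3.1.5 and 9.1).** CRc alpha 0.01. OS alpha 0.04, or 0.05 after CRc succeeds. MRD-negative CRc alpha 0.01 (only CRc significant), 0.04 (only OS) or 0.05 (both). Planned CRc power 90%. All levels are taken as two-sided. The OS alpha is the total over its looks, so the group-sequential boundaries do not affect the result.

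**The two primaries alone.** 0.01 + 0.04 = 0.05, so the fallback part reproduces. With both null and independent, the error is 0.01 + 0.99 x 0.04 = 0.0496. The CRc sample size also reproduces: 20% against 40% at alpha 0.01 needs 154 per arm, 308 in all, with power 0.9006.

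**All three endpoints: CRc effect, OS and MRD-negative CRc null.** With CRc certain to be significant, an error is a rejection of OS at 0.05 or, if OS is not rejected, of MRD-negative CRc at 0.01:

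0.05 + 0.95 x 0.01 = 1 - 0.95 x 0.99 = 0.0595 for independent tests. Whatever the dependence, the bound is 0.05 + 0.01 = 0.06.

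**Correlation and CRc power.** The documents give no correlation between the OS and MRD-negative CRc statistics, so a range is assumed and the bivariate normal probability that either test rejects is computed. When CRc is not significant, OS is tested at 0.04 and MRD-negative CRc only if OS has already been rejected, so that part contributes 0.04. With CRc independent of the other two, the 90%-power value is 0.9 x (middle column) + 0.1 x 0.04.

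| OS/MRD correlation | CRc certain | CRc power 90% |
|---|---|---|
| 0 | 0.0595 | 0.0576 |
| 0.3 | 0.0587 | 0.0568 |
| 0.5 | 0.0572 | 0.0555 |
| 0.7 | 0.0547 | 0.0532 |
| 0.9 | 0.0510 | 0.0499 |

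Under independence the error passes 0.05 once CRc power exceeds (0.05 - 0.04)/(0.0595 - 0.04), about 51%.

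**Simulation of the full rule** (4 million draws, CRc power 90%):

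- all independent: 0.0576
- CRc/MRD correlation 0.7, assumed because one endpoint is a subset of the other: 0.0545
- the same, with 0.3 for the other two pairs: 0.0539

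**False claims of benefit only.** 1 - 0.975 x 0.995 = 0.0299 against 0.025, an excess of at most about 0.005.

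**Other configurations under the stated rule.** OS effect only: 0.01 + 0.99 x 0.04 = 0.0496. All null: 0.0496. Both primaries effective, MRD-negative CRc null: 0.05. None exceeds 0.05.

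**The case against.** The strongest reply is that the rule is no longer in force. SAP 6.7 withdraws it in the section that states it. The branch also cannot be reached as planned: Protocol 9.3.1.9 requires 308 randomized patients and about 212 OS events before the primary CRc analysis, whereas enrollment closed at 240, before the first interim at about 106 events. This stands. It limits the practical weight, but both current documents still state an error rate that the procedure does not have, and SAP 9.1 records no change from the protocol.

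A second reply is that 0.0595 is an extreme. It needs CRc power near 1 and independent OS and MRD-negative CRc tests, and it counts false claims of harm as well as benefit. This is fair. The simulated cases at 90% power lie between 0.0539 and 0.0576, and at an OS/MRD correlation of 0.9 the excess is gone. But control at 0.05 has to hold in every configuration, and here it fails over most of the assumed range.

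A third is that other repairs exist. In this configuration, leaving OS at 0.04 gives 1 - 0.96 x 0.99 = 0.0496, and splitting the 0.01 equally gives 1 - 0.955 x 0.995 = 0.0498. Both keep a formal MRD-negative CRc test when only CRc succeeds, but both lower the OS level below the planned 0.05. That trade-off is the sponsor's choice.

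**Conclusion.** The concern holds. The planned rule does not control the overall type I error at 0.05 across the three endpoints. The maximum is 0.0595 (CRc power near 1, independent OS and MRD-negative CRc tests) and the dependence-free bound is 0.06. At the planned 90% CRc power the error is 0.0576 under independence and 0.0532 at an OS/MRD correlation of 0.7; the correlations are assumptions.

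The excess is modest and arises when CRc has an effect and OS and MRD-negative CRc have none. The primary-endpoint tests are not affected, nor is the descriptive final analysis. What needs correcting is the planned procedure and the property claimed for it.

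**What to change.** In Protocol 9.3.1.5 and SAP 6.7, replace the sentence covering a single significant primary with:

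> If only OS is significant, MRD-negative CRc will be tested at 0.04. If only CRc is significant, MRD-negative CRc will be reported descriptively.

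Keep 0.05 when both primaries are significant. Control then holds:

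- **CRc effect only:** rejecting MRD-negative CRc requires rejecting OS, which is already an error, so at most 0.05. At 90% CRc power it is 0.9 x 0.05 + 0.1 x 0.04 = 0.049; the three simulated cases give 0.0490, 0.0490 and 0.0488.
- **OS effect only:** at most 0.01 + 0.04 = 0.05.
- **Both effects:** at most 0.05.
- **All null:** at most 0.05, since rejecting MRD-negative CRc requires a primary rejection.

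In the SAP the inoperative paragraph may simply be deleted. Protocol 9.3 requires an amendment for an analysis change only if site conduct is altered, so the SAP edit can stand alone if the protocol is not otherwise reopened.

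Sample size and primary alphas do not change. The cost is the formal 0.01 test of MRD-negative CRc when only CRc is significant. A result at or below 0.01, which could have been claimed as soon as CRc succeeded, now waits for OS; one between 0.01 and 0.05 had to wait anyway.

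On timing, "The second interim analysis for OS will occur in conjunction with the primary analysis of CRc rate", at 212 of 354 events (0.599). Lan-DeMets O'Brien-Fleming-type spending of 0.025 per side gives z = 2.67 (two-sided nominal 0.0076). At hazard ratio 0.70 the expected z is 0.3567 x sqrt(212)/2 = 2.60, so OS crosses there with probability about 0.47. Applying the function directly to two-sided 0.05 gives z = 2.53 and about 0.53; the documents do not say which convention applies. Either way, about half the time the MRD-negative CRc test would wait for the final OS analysis.

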### **9.3.1.6 Data Transformations and Derivations**

For efficacy assessments, the date of response will be the latest of all applicable dates for the given assessment (e.g., bone marrow date, CBC date). The date of relapse/progression will be the earliest of all applicable dates for the given assessment. Detailed methodology will be provided in the SAP.

### **9.3.1.7 Analysis Sets**

The intent-to-treat (ITT) analysis set will include all randomized patients. Patients will be included in the treatment group assigned at randomization regardless of any actual treatment received.

The modified intent-to-treat (mITT) analysis set will include all patients from the ITT analysis set who receive any dose of blinded study treatment (vadastuximab talirine or placebo) or HMA. Patients will be included in the treatment group assigned at randomization regardless of the actual treatment received.

The safety analysis set will include all patients who receive any dose of blinded study treatment (vadastuximab talirine or placebo) or HMA. Treatment group will be determined using the actual treatment received, regardless of the randomization treatment assignment. Patients receiving any dose of vadastuximab talirine will be grouped into the experimental arm. Patients who do not receive vadastuximab talirine but receive any dose of HMA will be grouped into the comparator arm.

### **9.3.1.8 Examination of Subgroups**

As exploratory analyses, subgroup analyses may be conducted for selected endpoints, including, but not limited to gender, race, AML subtype, and randomization strata (cytogenetic risk, ECOG performance status, HMA, and age). Detailed methodology will be provided in the SAP.

### **9.3.1.9 Timing of Analyses**

The primary analysis of CRc rate is planned when the following 2 conditions are met: 1) 6 months after 308 patients have been randomized, and 2) approximately 212 OS events have occurred. The estimated duration of the study through the primary analysis of CRc rate is approximately 2 years from randomization of the first patient based on design assumptions. Only the first 308 patients randomized will be included in the primary analysis of CRc rate. CRc rate will also be analyzed for all randomized patients at the time of the final analysis.

The estimated duration of the study through the final analysis for OS is approximately 3 years from randomization of the first patient based on design assumptions.

There are 2 planned interim analyses of OS. The first interim analysis will take place when approximately 106 OS events have occurred (~30% of the targeted number of events) and will assess the futility of vadastuximab talirine in combination with azacitidine or decitabine.

The second interim analysis for OS will occur in conjunction with the primary analysis of CRc rate. The analysis will be conducted when the following 2 conditions are met: 1) 6 months after 308 patients have been randomized, and 2) approximately 212 OS events have occurred (~60% of the targeted number of events). The interim OS results will be assessed for early stopping for efficacy.

The IDMC will provide recommendations to the sponsor's Data Review Board as to appropriate study direction at the interim analysis.

End-of-trial is defined as the point at which all patients have died or discontinued the study, or have been followed for a maximum of 3 years after the last patient enrolled, whichever comes first. An end-of-trial analysis will be performed after study closure.

